6.2.2.17. Topical Corticosteroids Accountability

In part B, at every in-clinic visit following the baseline visit, the type, amount, and potency of TCS used will be recorded by site personnel. The amount of TCS used will be determined by weighing the tube at each visit through the end of the study.

In addition, caregivers will be asked to record TCS use daily, from start of 2-week TCS standardization period on day -14 through the end of the study, on an e-diary:

- Use of TCS (yes/no)
- Why did you not apply the topical corticosteroid to your child today?

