**Other secondary efficacy endpoints:**

- Proportion of patients with EASI-50 at week 16
- Proportion of patients with EASI-90 at week 16
- Change from baseline to week 16 in percent BSA affected by AD
- Percent change from baseline to week 16 in SCORAD
- Change from baseline to week 16 in weekly average of daily worst scratch/itch NRS score
- Proportion of patients with improvement (reduction) of weekly average of daily worst itch score  $\geq 4$  from baseline at week 16
- Proportion of patients with improvement (reduction) of weekly average of daily worst itch score  $\geq 3$  from baseline to week 16
- Change from baseline to week 16 in skin pain NRS
- Change from baseline to week 16 in patient's sleep quality NRS
- Change from baseline to week 16 in caregiver's sleep quality NRS
- Change from baseline to week 16 in health-related quality of life, as measured by CDLQI score (patients  $\geq 4$  years of age)
- Change from baseline to week 16 in health-related quality of life, as measured by IDQOL score (patients  $< 4$  years of age)
- Change from baseline to week 16 in Dermatitis Family Index, DFI score
- Change from baseline to week 16 in POEM score
- Topical treatment for AD – proportion of TCS medication-free days from baseline to week 16
- Mean weekly dose of low potency TCS through week 16
- Mean of caregiver missed workdays (CMW) from baseline to week 16

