#### Handling of dropouts or adjudicated rescue treatment or missing value for the binary response variables as the primary analysis:

- If a patient withdraws consent from the study or discontinues due to AE or lack of efficacy (LOE), this patient will be counted as a non-responder for the time points after withdrawal.
- To account for the impact of rescue treatment on the efficacy effect: if rescue treatment is used (see Section 4.3, Appendix 1, and Appendix 6 for rescue treatment), the patient will be specified as a non-responder from the time the rescue treatment is used.
- If the patient has the missing value at week 16 due to any other reasons including COVID-19, the data will be imputed using multiple imputation (MI) based on all observed values as described below:
- The underlying continuous (e.g. EASI) or categorical variable (e.g. IGA) will be imputed 40 times to generate 40 complete data sets by using the SAS procedure MI using the following steps.
  - **Step 1:** The monotone missing pattern is induced by Markov Chain Monte Carlo (MCMC) method in MI procedure using seed number 12345. The monotone missing pattern means that if a patient has missing value for a variable at a visit, then the values at all subsequent visits for the same variable are all missing for the patient.

- **Step 2:** The missing data at subsequent visits will be imputed using the regression method for the monotone pattern with seed number 54321 and adjustment for covariates including treatment groups, randomization strata (baseline weight group, baseline IGA and region), and relevant baseline variables. For the categorical variable, such as IGA, a logistic regression under monotone option will be used.

Based on each imputed data, the response status (responder or non-responder) will be determined for each subject.

Once imputations are made, the week 16 data (binary response) of each of the 40 complete datasets will be analyzed using CMH test. The SAS MIANALYZE procedure will be used to generate valid statistical inferences by combining results from the 40 analyses using Rubin's formula. An appropriate transformation (such as Wilson-Hilferty transformation) of CMH test statistics can be used in Rubin's formula (Ratitch et. al 2013).

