### **Mean weekly dose of low potency TCS**

The mean weekly dose of low potency TCS use during the treatment period endpoints will be analyzed using an ANCOVA model with treatment, randomization strata (baseline weight group, disease severity and region) and relevant baseline variables included in the model.

Similar analysis will be carried out for medium and/or high potency TCS.

Descriptive statistics will be provided for the mean of caregiver missed workdays (CMW) from baseline to week 16 for each treatment group.

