SCORing Atopic Dermatitis (SCORAD)	FAS	
Continuous:
 
 
% change from baseline
 
 
Categorical:
 
 
SCORAD50
 
SCORAD75
 
SCORAD90
 
	
 
Multiple imputation (MI) using pattern mixture (MI-WOCF) with ANCOVA for continuous variables
 
CMH test adjusted by randomization strata for categorical variables
 
	No	No
Dermatitis Family Index (DFI)	FAS	
 
Change from baseline
 
	Multiple imputation (MI) using pattern mixture (MI-WOCF) with ANCOVA	No	No
Global Individual Signs Score (GISS)	FAS	
 
Change from baseline
 
	Multiple imputation (MI) using pattern mixture (MI-WOCF) with ANCOVA for continuous variables	No	No
Patient Oriented Eczema Measure (POEM)	FAS	
 
Change from baseline
 
	
 
Multiple imputation (MI) using pattern mixture (MI-WOCF) with ANCOVA for continuous variables
 
	No	No

Parameter(s)	Analysis Populations	Endpoints	Primary Statistical Method	Supportive/Sensitivity Statistical Method	Subgroup Analysis
Children Dermatology Life Quality Index (CDLQI) ( $\geq 4$ years of age)	FAS	
 
Change from baseline
 
	
 
Multiple imputation (MI) using pattern mixture (MI-WOCF) with ANCOVA for continuous variables
 
	No	No
Infants' Dermatology Quality of Life Index (IDQOL) ( $< 4$ years of age)	FAS	
 
Change from baseline
 
	
 
Multiple imputation (MI) using pattern mixture (MI-WOCF) with ANCOVA for continuous variables
 
	No	No
TCS	FAS	
 
Proportion of TCS medication-free days from baseline to week 16
 
Mean weekly dose of TCS in grams for low potency TCS from baseline to week 16
 
	
 
CMH test adjusted randomization strata
 
ANCOVA for continuous variables
 
	No	No
Caregiver missed workdays (CMW)	FAS	
 
Mean of caregiver missed workdays
 
	
 
Descriptive statistics by visit/time
 
	No	No

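### SAP Appendix 2 assigns TCS-free days, a per-child fraction, to a CMH test that the SAP describes only for yes/no responses

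*SAP*

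**What the plan says.** Protocol Section 8.2.2 and SAP Section 4.4.2 list "proportion of TCS medication-free days from baseline to week 16" among the other secondary efficacy endpoints of Part B. Neither gives a denominator, a rule for missing days or a responder threshold.

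The data come from the e-diary. Under Protocol Section 6.2.2.17, "caregivers will be asked to record TCS use daily", as yes or no, from day -14 to the end of the study.

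The TCS row of SAP Appendix 2 has two endpoints and two methods, none of them labelled:

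- Endpoints: "Proportion of TCS medication-free days from baseline to week 16", then "Mean weekly dose of TCS in grams for low potency TCS from baseline to week 16".
- Methods: "CMH test adjusted randomization strata", then "ANCOVA for continuous variables".

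SAP Section 5.6.2 says: "The mean weekly dose of low potency TCS use during the treatment period endpoints will be analyzed using an ANCOVA model". It does not name a method for TCS-free days. The same section sends binary secondary endpoints to the procedure of Section 5.6.1 and continuous endpoints to ANCOVA, and Protocol Section 9.5.2.2 does likewise. In Section 5.6.1, each subject is first classed as responder or non-responder, and then "the week 16 data (binary response) of each of the 40 complete datasets will be analyzed using CMH test".

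**The concern.** The word proportion has two meanings in this plan. For IGA 0/1 or EASI-75 it is the share of children who respond, so each child contributes a yes or a no. For TCS-free days it is a share of one child's days, so each child contributes a number between 0 and 1. Appendix 2 appears to treat the second like the first.

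The rules that come with the CMH procedure do not carry over either. Counting a child as a non-responder from the time of rescue has no defined meaning for a fraction of days. Whoever programs the row must therefore choose an analysis that the SAP does not state, and the possible choices answer different questions. What is at stake is one of the plan's measures of steroid sparing. The SAP calls that effect clinically relevant when it adds a related TCS dose endpoint in Section 1.2.3.

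**Working it through.** The documents give no power, sample size or other figure for this endpoint, so there is none to reproduce. The check compares endpoint type with assigned method, then looks at what each way of running the test would do.

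**1. Which method belongs to which endpoint.** The pairing is read from bullet order. Two places support it. Section 5.6.2 ties ANCOVA to weekly dose, which leaves CMH for TCS-free days. The SCORAD row of the same table also follows order: its continuous endpoint and ANCOVA come first, its categorical endpoints and CMH second.

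**2. What type of endpoint it is.** Treatment runs from day 1 to the week 16 visit on day 113, so there are 113 - 1 = 112 diary days. Intermediate values are built into the regimen: Protocol Section 5.2 steps TCS down from daily use to three times a week before stopping, and a week with three applications has (7 - 3)/7 = 57% free days. The outcome is graded and no cut-off makes it binary.

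**3. Ways to run a CMH test on it.**

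- Dichotomize the fraction. This needs a cut-point, and none is given.
- Count days as units. This treats up to 112 correlated days per child as independent.
- Use a row-mean-score or rank form with one value per child. This is valid, but the SAP does not specify it.

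**4. Size of the problem if days were pooled.** With m = 112 days per child and within-child correlation ICC, the design effect is DE = 1 + (m - 1) × ICC = 1 + 111 × ICC. The true error of a nominal two-sided 5% test is about 2 × [1 - Φ(1.96/√DE)]. For ICC = 0.2, DE = 1 + 22.2 = 23.2, √DE = 4.82, 1.96/4.82 = 0.407, and the error is 2 × (1 - 0.658) = 0.68.

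A simulation with no treatment effect was run alongside: 160 children, 8 equal strata of 20, 112 beta-binomial days each, mean TCS-free share 20%, 4000 runs. The ICC values, the 20% and the equal strata are assumptions.

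| ICC (assumed) | DE | Error, formula | Error, simulated |
|---|---|---|---|
| 0.02 | 3.2 | 0.27 | 0.28 |
| 0.05 | 6.6 | 0.44 | 0.45 |
| 0.1 | 12.1 | 0.57 | not run |
| 0.2 | 23.2 | 0.68 | 0.67 |
| 0.5 | 56.5 | 0.79 | 0.81 |

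**5. One value per child.** In the same simulated data, stratified mean-score and rank tests on the child's fraction had type I error of 0.046 to 0.055. The simulation standard error is √(0.05 × 0.95/4000) = 0.0034, so these agree with 0.05. ANCOVA also uses one value per child; it was not simulated.

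**The case against.** The case on the other side has four parts.

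- **The general rule may already cover the endpoint.** Section 5.6.2 sends continuous endpoints to ANCOVA and gives its examples as non-exhaustive. On that reading Appendix 2 is only a summary table that disagrees with the governing text. This is fair: the plan is not without a method. But the table is the only place that assigns a method to this endpoint, and it points the other way.
- **The pairing is inferred.** The EASI and itch rows label both columns as categorical or continuous; the TCS row does not, and no sentence assigns CMH to TCS-free days. This stands as a caveat, but order, Section 5.6.2 and the SCORAD row all lead to the same reading.
- **CMH is not wrong in every form.** A row-mean-score or van Elteren version is valid, as step 5 shows. The defect is that the only form described takes a binary response.
- **The endpoint carries no alpha.** It is not among the 16 steps in SAP Section 5.6.3. This is correct and limits the consequence.

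A reader might infer that the planned test has a type I error of 57% to 79%, the formula values for ICC 0.1 to 0.5. The documents do not support that. The SAP nowhere proposes pooling days, the full analysis set consists of randomized patients, and Section 5.6.1 determines response for each subject. A reader might also infer that any cut-point would be post hoc. That is not established, because Section 1 says the SAP will be finalized before database lock, and a threshold set by then would be pre-specified.

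**Conclusion.** The concern holds as a conflict within the plan. Appendix 2 gives a per-child fraction to a procedure described for binary responses, against the ANCOVA rule for continuous endpoints in both documents. This goes beyond missing detail, because following the table leads to a different analysis from following the general rule.

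The consequence is confined to one secondary endpoint. The primary, co-primary and key secondary results and the family-wise error do not depend on it. No single error rate can be attached to the plan as written: the error is nominal if one value per child is tested, and inflated only if days are pooled, by an amount that depends on an ICC the documents do not give. The conclusion rests on reading the TCS row in bullet order. It should be corrected, but it does not threaten the trial's main conclusions.

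**What to change.** In the TCS row of SAP Appendix 2 and in Section 5.6.2:

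- **Define the variable.** For each child, TCS-free days divided by days with a diary entry, from baseline to week 16. State how missing diary days are handled and how days after rescue count.
- **Assign the analysis.** ANCOVA on the per-child fraction with treatment and the three randomization factors (weight group, baseline IGA, region), reporting the mean difference and 95% CI. Add a baseline covariate only if one is defined. The standardization period could supply one, but inclusion criterion 11 requires at least 11 of 14 daily applications, which leaves at most 14 - 11 = 3 free days and little to adjust for.
- **Pre-specify one sensitivity analysis.** A stratified rank test (van Elteren), with the two-patient stratum merged as in Section 5.6.1. Fixing this in advance is better than switching method if the data look skewed, which would make the choice data-dependent.
- **If a responder version is intended,** state its threshold before unblinding; the CMH procedure of Section 5.6.1 could then be used.

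The cost is one table row and a short paragraph. The diary data are already collected, and sample size and power do not change.

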**Safety Analyses:**

Endpoint	Analysis Populations	Statistical Method	Supportive Analysis	Subgroup Analysis	Other Analyses
Adverse Events	SAF	Descriptive statistics	No	Yes for selected AE summary	No
Skin infection TEAE	SAF	Incidence of skin infection TEAE (excluding herpetic infections) through week 16	Descriptive summary (incidence)	No	No
TE-SAE	SAF	Incidence of treatment-emergent serious adverse events (SAE) through week 16	Descriptive summary (incidence)	No	No
Laboratory Measures	SAF	Descriptive Statistics	No	No	No
Vital sign	SAF	Descriptive Statistics	No	No	No
ECG	SAF	Descriptive Statistics	No	No	No

**APPENDIX 3. SCHEDULE OF EVENTS FOR THE SCREENING, TREATMENT, AND FOLLOW-UP PERIOD (PART B)**

Study Procedure	Screening Period 		B L	Treatment Period																	Follow-Up			Un-schedule d Visit 	ET Visit
	SC N	TC S Std					P V 		P V 	P V 	P V 		P V 	P V 	P V 		P V 	P V 	P V 	EO T			EOS		
Visit	1	2	3	4	5	6 	7	8 	9	10 	11	12 	13 	14 	15	16	17	18	19	20	21	22			
Week	-	-		1	2	3	4	5	6	7	8	9	10	11	12	13	14	15	16	20	24	28			
Study Day(s)	-56 to -15	-14 to -1	1	8	15	22	29	36	43	50	57	64	71	78	85	92	99	106	113	141	169	197			
Visit window (days)	-	-		±3	±3	±3	±3	±3	±3	±3	±3	±3	±3	±3	±3	±3	±3	±3	±3	±4	±4	±4			
Screening/Baseline:																									
Inclusion/Exclusion 	X		X																						
Parental Informed Consent 	X																								

Study Procedure	Screening Period 		B L	Treatment Period																	Follow-Up			Un- schedule d Visit 	ET Visit
	SC N	TC S Std				P V 		P V 	P V 	P V 		P V 	P V 	P V 		P V 	P V 	P V 	EO T			EOS			
Visit	1	2	3	4	5	6 	7	8 	9	10 	11	12 	13 	14 	15	16	17	18	19	20	21	22			
Week	-	-		1	2	3	4	5	6	7	8	9	10	11	12	13	14	15	16	20	24	28			
Study Day(s)	-56 to -15	-14 to -1	1	8	15	22	29	36	43	50	57	64	71	78	85	92	99	106	113	141	169	197			
Visit window (days)	-	-		±3	±3	±3	±3	±3	±3	±3	±3	±3	±3	±3	±3	±3	±3	±3	±3	±4	±4	±4			
Parental Informed Consent for Optional Genomic Sub-study 	X																								
Parental Informed Consent for Optional Vaccine Sub-study 	X																								

Study Procedure	Screening Period 		B L	Treatment Period																	Follow-Up			Un-schedule d Visit 	ET Visit
	SC N	TC S Std				P V 		P V 	P V 	P V 		P V 	P V 	P V 		P V 	P V 	P V 	EO T			EOS			
Visit	1	2	3	4	5	6 	7	8 	9	10 	11	12 	13 	14 	15	16	17	18	19	20	21	22			
Week	-	-		1	2	3	4	5	6	7	8	9	10	11	12	13	14	15	16	20	24	28			
Study Day(s)	-56 to -15	-14 to -1	1	8	15	22	29	36	43	50	57	64	71	78	85	92	99	106	113	141	169	197			
Visit window (days)	-	-		±3	±3	±3	±3	±3	±3	±3	±3	±3	±3	±3	±3	±3	±3	±3	±3	±4	±4	±4			
Parental Informed Consent for Optional Tape Stripping Sub-study (selected study sites only)	X																								

Study Procedure	Screening Period 		B L	Treatment Period																	Follow-Up			Un- schedule d Visit 	ET Visit
	SC N	TC S Std				P V 		P V 	P V 	P V 		P V 	P V 	P V 		P V 	P V 	P V 	EO T			EOS			
Visit	1	2	3	4	5	6 	7	8 	9	10 	11	12 	13 	14 	15	16	17	18	19	20	21	22			
Week	-	-		1	2	3	4	5	6	7	8	9	10	11	12	13	14	15	16	20	24	28			
Study Day(s)	-56 to -15	-14 to -1	1	8	15	22	29	36	43	50	57	64	71	78	85	92	99	106	113	141	169	197			
Visit window (days)	-	-		±3	±3	±3	±3	±3	±3	±3	±3	±3	±3	±3	±3	±3	±3	±3	±3	±4	±4	±4			
Parental Informed Consent for Optional Use of Photographs (selected study sites only) 	X																								
Collect vaccination plan 	X																								

Study Procedure	Screening Period 		B L	Treatment Period																	Follow-Up			Un-schedule d Visit 	ET Visit
	SC N	TC S Std				P V 		P V 	P V 	P V 		P V 	P V 	P V 		P V 	P V 	P V 	EO T			EOS			
Visit	1	2	3	4	5	6 	7	8 	9	10 	11	12 	13 	14 	15	16	17	18	19	20	21	22			
Week	-	-		1	2	3	4	5	6	7	8	9	10	11	12	13	14	15	16	20	24	28			
Study Day(s)	-56 to -15	-14 to -1	1	8	15	22	29	36	43	50	57	64	71	78	85	92	99	106	113	141	169	197			
Visit window (days)	-	-		±3	±3	±3	±3	±3	±3	±3	±3	±3	±3	±3	±3	±3	±3	±3	±3	±4	±4	±4			
Medical History	X																								
Ophthalmology Exam (patients with history of certain eye disorders) 	X																								
Demographics	X																								

Study Procedure	Screening Period 		B L	Treatment Period																	Follow-Up			Un-schedule d Visit 	ET Visit
	SC N	TC S Std				P V 		P V 	P V 	P V 		P V 	P V 	P V 		P V 	P V 	P V 	EO T			EOS			
Visit	1	2	3	4	5	6 	7	8 	9	10 	11	12 	13 	14 	15	16	17	18	19	20	21	22			
Week	-	-		1	2	3	4	5	6	7	8	9	10	11	12	13	14	15	16	20	24	28			
Study Day(s)	-56 to -15	-14 to -1	1	8	15	22	29	36	43	50	57	64	71	78	85	92	99	106	113	141	169	197			
Visit window (days)	-	-		±3	±3	±3	±3	±3	±3	±3	±3	±3	±3	±3	±3	±3	±3	±3	±3	±4	±4	±4			
Randomization			X																						
Parent/Caregiver e-diary training 	X	X																							
Treatment:																									
TCS application 		X	X	X	X	X	X	X	X	X	X	X	X	X	X	X	X	X	X	X	X	X			

Study Procedure	Screening Period 		B L	Treatment Period																	Follow-Up			Un-schedule d Visit 	ET Visit
	SC N	TC S Std				P V 		P V 	P V 	P V 		P V 	P V 	P V 		P V 	P V 	P V 	EO T			EOS			
Visit	1	2	3	4	5	6 	7	8 	9	10 	11	12 	13 	14 	15	16	17	18	19	20	21	22			
Week	-	-		1	2	3	4	5	6	7	8	9	10	11	12	13	14	15	16	20	24	28			
Study Day(s)	-56 to -15	-14 to -1	1	8	15	22	29	36	43	50	57	64	71	78	85	92	99	106	113	141	169	197			
Visit window (days)	-	-		±3	±3	±3	±3	±3	±3	±3	±3	±3	±3	±3	±3	±3	±3	±3	±3	±4	±4	±4			
TCS dispensation		X	X	X	X		X				X				X				X	X	X		X		
TCS accountability 			X	X	X		X				X				X				X	X	X	X	X	X	
Administer Study Drug 			X 				X 				X 				X										

Study Procedure	Screening Period 		B L	Treatment Period																	Follow-Up			Un- schedule d Visit 	ET Visit
	SC N	TC S Std				P V 		P V 	P V 	P V 		P V 	P V 	P V 		P V 	P V 	P V 	EO T			EOS			
Visit	1	2	3	4	5	6 	7	8 	9	10 	11	12 	13 	14 	15	16	17	18	19	20	21	22			
Week	-	-		1	2	3	4	5	6	7	8	9	10	11	12	13	14	15	16	20	24	28			
Study Day(s)	-56 to -15	-14 to -1	1	8	15	22	29	36	43	50	57	64	71	78	85	92	99	106	113	141	169	197			
Visit window (days)	-	-		±3	±3	±3	±3	±3	±3	±3	±3	±3	±3	±3	±3	±3	±3	±3	±3	±4	±4	±4			
Parent/ Caregiver Counseling for e-diary Completion		X	X	X	X		X				X				X				X	X	X		X		
Parent / Caregiver Recording of TCS Use via e-diary (daily)		X	X	X	X	X	X	X	X	X	X	X	X	X	X	X	X	X	X	X	X	X	X	X	X

Study Procedure	Screening Period 		B L	Treatment Period																	Follow-Up			Un- schedule d Visit 	ET Visit
	SC N	TC S Std				P V 		P V 	P V 	P V 		P V 	P V 	P V 		P V 	P V 	P V 	EO T			EOS			
Visit	1	2	3	4	5	6 	7	8 	9	10 	11	12 	13 	14 	15	16	17	18	19	20	21	22			
Week	-	-		1	2	3	4	5	6	7	8	9	10	11	12	13	14	15	16	20	24	28			
Study Day(s)	-56 to -15	-14 to -1	1	8	15	22	29	36	43	50	57	64	71	78	85	92	99	106	113	141	169	197			
Visit window (days)	-	-		±3	±3	±3	±3	±3	±3	±3	±3	±3	±3	±3	±3	±3	±3	±3	±3	±4	±4	±4			
Parent / Caregiver Recording of Emollient Use via e-diary (daily)	X	X	X	X	X	X	X	X	X	X	X	X	X	X	X	X	X	X	X	X	X	X	X	X	
Concomitant Meds and Procedures	X	X	X	X	X	X	X	X	X	X	X	X	X	X	X	X	X	X	X	X	X	X	X	X	
Efficacy  :																									

Study Procedure	Screening Period 		B L	Treatment Period																	Follow-Up			Un- schedule d Visit 	ET Visit
	SC N	TC S Std				P V 		P V 	P V 	P V 		P V 	P V 	P V 		P V 	P V 	P V 	EO T			EOS			
Visit	1	2	3	4	5	6 	7	8 	9	10 	11	12 	13 	14 	15	16	17	18	19	20	21	22			
Week	-	-		1	2	3	4	5	6	7	8	9	10	11	12	13	14	15	16	20	24	28			
Study Day(s)	-56 to -15	-14 to -1	1	8	15	22	29	36	43	50	57	64	71	78	85	92	99	106	113	141	169	197			
Visit window (days)	-	-		±3	±3	±3	±3	±3	±3	±3	±3	±3	±3	±3	±3	±3	±3	±3	±3	±4	±4	±4			
Assessment of Pruritus (worst scratch/itch) NRS 	X	X	X	X	X	X	X	X	X	X	X	X	X	X	X	X	X	X	X	X	X	X	X	X	
Assessment of Skin Pain NRS and Sleep Diary 			X	X	X		X												X			X			

Study Procedure	Screening Period 		B L	Treatment Period																	Follow-Up			Un-schedule d Visit 	ET Visit
	SC N	TC S Std					P V 		P V 	P V 	P V 		P V 	P V 	P V 		P V 	P V 	P V 	EO T			EOS		
Visit	1	2	3	4	5	6 	7	8 	9	10 	11	12 	13 	14 	15	16	17	18	19	20	21	22			
Week	-	-		1	2	3	4	5	6	7	8	9	10	11	12	13	14	15	16	20	24	28			
Study Day(s)	-56 to -15	-14 to -1	1	8	15	22	29	36	43	50	57	64	71	78	85	92	99	106	113	141	169	197			
Visit window (days)	-	-		±3	±3	±3	±3	±3	±3	±3	±3	±3	±3	±3	±3	±3	±3	±3	±3	±4	±4	±4			
IGA, EASI, SCORAD, BSA, GISS	X		X	X	X		X				X				X				X	X	X	X	X	X	
CDLQI   IDQOL   , DFI  POEM  Caregiver Missed Workdays	X		X		X		X				X				X				X	X	X	X	X	X	

Study Procedure	Screening Period 		B L	Treatment Period																	Follow-Up			Un-schedule d Visit 	ET Visit
	SC N	TC S Std				P V 		P V 	P V 	P V 		P V 	P V 	P V 		P V 	P V 	P V 	EO T			EOS			
Visit	1	2	3	4	5	6 	7	8 	9	10 	11	12 	13 	14 	15	16	17	18	19	20	21	22			
Week	-	-		1	2	3	4	5	6	7	8	9	10	11	12	13	14	15	16	20	24	28			
Study Day(s)	-56 to -15	-14 to -1	1	8	15	22	29	36	43	50	57	64	71	78	85	92	99	106	113	141	169	197			
Visit window (days)	-	-		±3	±3	±3	±3	±3	±3	±3	±3	±3	±3	±3	±3	±3	±3	±3	±3	±4	±4	±4			
CGID	X		X		X		X				X				X				X	X	X	X	X	X	
CGIC					X		X				X				X				X	X	X	X	X	X	
PASQ 	X		X				X												X			X	X	X	
CNSQ 			X				X												X			X			

Study Procedure	Screening Period 		B L	Treatment Period																	Follow-Up			Un-schedule d Visit 	ET Visit
	SC N	TC S Std				P V 		P V 	P V 	P V 		P V 	P V 	P V 		P V 	P V 	P V 	EO T			EOS			
Visit	1	2	3	4	5	6 	7	8 	9	10 	11	12 	13 	14 	15	16	17	18	19	20	21	22			
Week	-	-		1	2	3	4	5	6	7	8	9	10	11	12	13	14	15	16	20	24	28			
Study Day(s)	-56 to -15	-14 to -1	1	8	15	22	29	36	43	50	57	64	71	78	85	92	99	106	113	141	169	197			
Visit window (days)	-	-		±3	±3	±3	±3	±3	±3	±3	±3	±3	±3	±3	±3	±3	±3	±3	±3	±4	±4	±4			
Photograph AD Areas (Selected Study Sites only)			X																X			X		X	

Study Procedure	Screening Period 		B L	Treatment Period																	Follow-Up			Un-schedule d Visit 	ET Visit
	SC N	TC S Std				P V 		P V 	P V 	P V 		P V 	P V 	P V 		P V 	P V 	P V 	EO T			EOS			
Visit	1	2	3	4	5	6 	7	8 	9	10 	11	12 	13 	14 	15	16	17	18	19	20	21	22			
Week	-	-		1	2	3	4	5	6	7	8	9	10	11	12	13	14	15	16	20	24	28			
Study Day(s)	-56 to -15	-14 to -1	1	8	15	22	29	36	43	50	57	64	71	78	85	92	99	106	113	141	169	197			
Visit window (days)	-	-		±3	±3	±3	±3	±3	±3	±3	±3	±3	±3	±3	±3	±3	±3	±3	±3	±4	±4	±4			
Safety:																									
Weight	X		X																X			X		X	
Height	X																		X			X		X	
Vital Signs	X		X 15	X	X		X 15				X 15				X				X	X	X	X	X	X	
Physical Examination	X		X																X			X	X	X	
ECG 	X																		X			X	X	X	

Study Procedure	Screening Period 		B L	Treatment Period																	Follow-Up			Un-schedule d Visit 	ET Visit
	SC N	TC S Std				P V 		P V 	P V 	P V 		P V 	P V 	P V 		P V 	P V 	P V 	EO T			EOS			
Visit	1	2	3	4	5	6 	7	8 	9	10 	11	12 	13 	14 	15	16	17	18	19	20	21	22			
Week	-	-		1	2	3	4	5	6	7	8	9	10	11	12	13	14	15	16	20	24	28			
Study Day(s)	-56 to -15	-14 to -1	1	8	15	22	29	36	43	50	57	64	71	78	85	92	99	106	113	141	169	197			
Visit window (days)	-	-		±3	±3	±3	±3	±3	±3	±3	±3	±3	±3	±3	±3	±3	±3	±3	±3	±4	±4	±4			
Adverse Events 	X	X	X 15	X	X	X	X 15	X	X	X	X	X	X	X	X	X	X	X	X	X	X	X	X	X	
Laboratory Testing:																									
Hematology	X						X												X			X	X	X	
Blood Chemistry	X						X												X			X	X	X	

Study Procedure	Screening Period 		B L	Treatment Period																	Follow-Up			Un-schedule d Visit 	ET Visit
	SC N	TC S Std					P V 		P V 	P V 	P V 		P V 	P V 	P V 		P V 	P V 	P V 	EO T			EOS		
Visit	1	2	3	4	5	6 	7	8 	9	10 	11	12 	13 	14 	15	16	17	18	19	20	21	22			
Week	-	-		1	2	3	4	5	6	7	8	9	10	11	12	13	14	15	16	20	24	28			
Study Day(s)	-56 to -15	-14 to -1	1	8	15	22	29	36	43	50	57	64	71	78	85	92	99	106	113	141	169	197			
Visit window (days)	-	-		±3	±3	±3	±3	±3	±3	±3	±3	±3	±3	±3	±3	±3	±3	±3	±3	±4	±4	±4			
HIV, HBsAg, HBsAb, HBcAb, Hepatitis C Ab, TB 	X																								
Serum sample for vaccination response 		X	X	X	X		X				X				X				X	X	X	X	X	X	
Biomarkers:																									

Study Procedure	Screening Period 		B L	Treatment Period																	Follow-Up			Un-schedule d Visit 	ET Visit
	SC N	TC S Std				P V 		P V 	P V 	P V 		P V 	P V 	P V 		P V 	P V 	P V 	EO T			EOS			
Visit	1	2	3	4	5	6 	7	8 	9	10 	11	12 	13 	14 	15	16	17	18	19	20	21	22			
Week	-	-		1	2	3	4	5	6	7	8	9	10	11	12	13	14	15	16	20	24	28			
Study Day(s)	-56 to -15	-14 to -1	1	8	15	22	29	36	43	50	57	64	71	78	85	92	99	106	113	141	169	197			
Visit window (days)	-	-		±3	±3	±3	±3	±3	±3	±3	±3	±3	±3	±3	±3	±3	±3	±3	±3	±4	±4	±4			
TARC			X				X												X			X		X	
Serum Immunoglobulin profiling, antigen-specific IgE			X																X			X		X	

Study Procedure	Screening Period 		B L	Treatment Period																	Follow-Up			Un- schedule d Visit 	ET Visit
	SC N	TC S Std				P V 		P V 	P V 	P V 		P V 	P V 	P V 		P V 	P V 	P V 	EO T			EOS			
Visit	1	2	3	4	5	6 	7	8 	9	10 	11	12 	13 	14 	15	16	17	18	19	20	21	22			
Week	-	-		1	2	3	4	5	6	7	8	9	10	11	12	13	14	15	16	20	24	28			
Study Day(s)	-56 to -15	-14 to -1	1	8	15	22	29	36	43	50	57	64	71	78	85	92	99	106	113	141	169	197			
Visit window (days)	-	-		±3	±3	±3	±3	±3	±3	±3	±3	±3	±3	±3	±3	±3	±3	±3	±3	±4	±4	±4			
Research Testing  :																									
Optional DNA buccal sample 			X																						
Optional tape stripping sample 			X																X						
PK/Drug Concentration and ADA Samples  :																									

Study Procedure	Screening Period 		B L	Treatment Period																	Follow-Up			Un- schedule d Visit 	ET Visit
	SC N	TC S Std				P V 		P V 	P V 	P V 		P V 	P V 	P V 		P V 	P V 	P V 	EO T			EOS			
Visit	1	2	3	4	5	6 	7	8 	9	10 	11	12 	13 	14 	15	16	17	18	19	20	21	22			
Week	-	-		1	2	3	4	5	6	7	8	9	10	11	12	13	14	15	16	20	24	28			
Study Day(s)	-56 to -15	-14 to -1	1	8	15	22	29	36	43	50	57	64	71	78	85	92	99	106	113	141	169	197			
Visit window (days)	-	-		±3	±3	±3	±3	±3	±3	±3	±3	±3	±3	±3	±3	±3	±3	±3	±3	±4	±4	±4			
PK/Drug concentration sample 			X				X				X				X				X	X		X	X	X	
ADA sample 			X																X			X	X	X	

Note: AD = atopic dermatitis; ADA = anti0drug antibody; AESI=adverse event of special interest; BL = Baseline; BSA = body surface area; CDLQI = Childrens’ Dermatology Life Quality Index; CGIC = Caregiver Global Impression of Change; CGID = Caregiver Global Impression of Disease; CNSQ = Caregiver-Reported Nasal Symptom Questionnaire; DFI = Dermatitis Family Index; EASI = Eczema Area and Severity Index; ECG = electrocardiogram; e-diary = electronic diary; EOT = End of treatment; EOS = End of Study; ET = Early Termination; GISS = Global Individual Signs Score; HBcAb = hepatitis B core antibody; HBsAb = hepatitis B surface antibody; HBsAg = hepatitis B surface antigen; HIV = human immunodeficiency virus; ICF = informed consent form; IDQOL = Infants’ Dermatology Quality of Life Index; IGA = Investigator Global Assessment; IgE = immunoglobulin E; NRS = numeric rating scale; PASQ = Pediatric Asthma Symptom Questionnaire; PK = pharmacokinetic; POEM = Patient Oriented Eczema Measure; PV = phone visit; Q4W = every 4 weeks; SCN = screening; SCORAD = SCORing Atopic Dermatitis; TARC = thymus and activation regulated chemokine; TB = tuberculosis; TCS = topical corticosteroid; Std = standardization.

-  The site will contact the parent/caregiver by telephone to conduct these visits.
-  For patients whose parents or legal guardians agree to their participation and provide a specific written informed consent for the optional genomics sub-study (DNA sample collection), DNA sample should be collected at the day 1 visit but can be collected at any visit during the study.
-  Parents/caregivers of patients will be encouraged to provide vaccination plans for any vaccines which are in line with the patient's age, and local medical practice (live attenuated vaccines are excluded) during the study. Parents or legal guardians of patients planning to receive any vaccines during the study may optionally sign a separate informed consent for collection of 2 blood samples (a pre-vaccine and post-vaccine sample) for assay of vaccine IgG in serum for each vaccination.
-  The study team on site will collect information from the parents/caregivers regarding the vaccinations planned during the next 6 months from screening. The study team should refer to the patient's medical records and national vaccination schedule to gather this information. The study team can also contact the patient's primary physician and/or pediatrician to gather this information.
-  Training of parents/caregivers regarding completion of e-diary at visit 1 to record a) completion of assessment of pruritus NRS (worst scratch/itch scale), skin pain NRS, sleep diary, and CNSQ and b) TCS and emollient usage. Provide additional training as necessary based on review of e-diary use.
-  As per the standardized regimen outlined in Section 5.2 of the study protocol.
-  The type, amount, and potency of topical products used during the study will be recorded. The amount of TCS used will be determined by weighing the tube at each visit through the end of the study.
-  The dose regimens, including frequency of administration in part B are placebo Q4W or dupilumab Q4W tiered fixed-dose (200 mg for patients  $\geq 5$ - $<15$ kg or 300 mg for patients  $\geq 15$ - $<30$  kg).
-  Patients will be monitored at the study site at visits 3, 7 and 11 for a minimum of 2 hours after study drug administration.
-  Assessments/procedures should be conducted in the following order: patient reported outcomes, investigator assessments, safety and laboratory assessments, administration of study drug.
-  The assessment will be recorded daily. Parents/caregivers will complete an e-diary daily to record pruritus (worst scratch/itch) NRS in patients.
-  The questionnaires will be administered only to those patients and/or parents/caregivers who speak fluently the language in which the questionnaire is presented (based on availability of validated translations in participating countries). It is recommended that the same person complete the questionnaire on behalf of the patient throughout the study.
-  Childrens' Dermatology Life Quality Index (CDLQI) for patients  $\geq 4$  years of age, Infants' Dermatitis Quality of Life Index (IDQOL) for patients  $<4$  years of age, Dermatology Family Index (DFI) to be completed by an adult family member of a child affected by dermatitis.
-  Questionnaire will be completed by the parent/caregiver on behalf of the patient. It is recommended that the same person complete the questionnaire on behalf of the patient throughout the study.
-  Patients will be monitored at the study site at visits 3, 7, and 11 for a minimum of 2 hours after study drug administration. Vital signs (sitting systolic and diastolic blood pressures, heart rate, respiratory rate, and body temperature) and AE assessments will be done at 30 minutes ( $\pm 10$  minutes) post-injection, and then at 2 hours ( $\pm 15$  minutes) post-injection.
-  Samples will be collected before the injection of study drug.
-  TB testing will be performed on a country-by-country basis, according to local guidelines, if required by regulatory authorities or ethics boards.
-  Optional collection of blood for assay of vaccine IgG in serum for each vaccine administered. The first sample should be drawn within 6 weeks prior to vaccination, and the second sample should be drawn 3 to 4 weeks (maximum 6 weeks) after vaccination. Vaccinations should be performed in compliance with the patient's recommended immunization schedule. Blood collections should be conducted at regularly scheduled study visits but, if this is not feasible, samples can also be drawn at unscheduled visits.
-  Samples to measure functional dupilumab concentration and biomarkers will be collected prior to injection of study drug.
-  Samples to be collected prior to injection of study drug. Patients who are ADA positive at their last study visit (early termination, or end of study) and who do not participate in the OLE may be considered for follow-up based on the overall clinical presentation at that time. Patients who are considered for follow-up may be asked to return to the clinic to have additional samples collected for analysis.
-  The specific assessments that will be performed at the unscheduled visit will depend upon the reason for the unscheduled visit. In the event of suspected SAEs, such as anaphylaxis or hypersensitivity, additional PK and ADA samples may be collected at or near to the event as practically possible.
-  Eligibility based on age at time of screening visit.

-  Assent collected from patient, if applicable, as per local regulatory (competent authority/ethics) guidelines, based upon the age and level of maturity of the patient.
-  The length of the screening period is not fixed but must not exceed 56 days (including TCS standardization). The length of the TCS standardization period is fixed at 14 days.
-  Any unused serum samples collected for dupilumab concentrations or ADA measurements may be used for exploratory biomarker research related to AD, inhibition of the IL-4R $\alpha$  pathway with an antibody, treatment response (PD and or predictive), or vaccine response, as well as to investigate unexpected AEs or to identify markers associated with adverse reactions.
-  Pain and sleep will be assessed daily for the 14 days leading up to the baseline visit, the 7 days leading up to the week 1 visit, the 7 days leading up to the week 2 visit, the 7 days leading up to the week 4 visit, the 7 days leading up to the week 16 visit, and 7 days leading up to the week 28 visit. Parents/caregivers will complete a daily e-diary on these days to record skin pain and sleep in patients.
-  ECGs should be conducted prior to collection of blood samples at visits requiring blood draws.
-  Completed only for the subset of patients with ongoing asthma.
-  Completed only for the subset of patients with a medical history of allergic rhinitis. Caregivers will be instructed on using the e-diary to record the CNSQ for 14 days before baseline/day 1 and for the 7 days preceding visits 7, 19, and 22 (weeks 4, 16, and 28).
-  Optional parental informed consent for use of photographs for educational/marketing purposes (selected study sites only).
-  An optional tape stripping sub-study may be performed at a subset of study sites. Parents or legal guardians who agree for their child to participate in the tape stripping sub-study will be required to sign a separate sub-study ICF before collection of the samples. Baseline samples should be collected on day 1/baseline (pre-dose). A second sample will be collected at week 16.
-  Patients who have history of certain eye disorders (conjunctivitis, blepharitis or keratitis) within 12 months prior to the screening visit will be referred to an ophthalmologist (see protocol Section 6.2.3.6). Any baseline findings will be documented as part of the patient's medical history and/or physical exam, as appropriate.
-  Any patient who experiences an AESI related to an eye disorder will be referred to an ophthalmologist (see protocol Section 7.2.3).

